RT-PCR tests on D4, D7, D10, and D28, and at any unscheduled visits. Secondary endpoints analyses: RT-PCR tests on D4, D7, D10, and D28, and at any unscheduled visits. WHO COVID-19 and News 2 scales scoring on D1, D10, and D28, and at any unscheduled visits. COVID-19 related AE notification by participants and/or investigators throughout the study. COVID-19 related hospitalisations notified by the investigators. Duration of hospitalisation as calculated from the associated SAE notification form (date of hospital admission through to date of hospital release). COVID-19 related deaths notified by the investigators. AE notification by participants or detection by investigators. **Concomitant Medication:** Prohibited medications: The following medications are prohibited: Inhibitors of p-glycoprotien, e.g. amiodarone, azithromycin, ketoconazole, cyclosporine up to 28 days prior to randomization and throughout the study. Current pain medications such as acetylsalicylic acid or metamizol. Precautions: Some medications may have moderate or minor interactions with ivermectin. **Endpoints:** Primary endpoint: Proportion of laboratory-confirmed COVID-19 infections between baseline and Day 28. Secondary endpoints: Time to change from baseline in negative RT-PCR to positive RT-PCR. Change from baseline in the WHO-COVID 19 and NEWS-2 scores. Time to change from baseline to first COVID-19 related clinical events. Proportion of COVID-19 related hospitalisations. Proportion of COVID-19 related mortality. Safety and Tolerability of ivermectin based on treatment emergent adverse events (TEAE) and serious adverse events (SAE) according to Common

Clinical Protocol

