- (c) IMP will be administered as follows: 200 µg/kg as the loading dose admisnistered on D1at the study site, and then 100 µg/kg/day for 27 days taken by the participant at home.
- (d) PCR test to be performed on D1, D4, D7, D10 and D28: sequencing and viral load. In addition, any unscheduled test performed by the participant during the study will also be collected. Confirmed negative participants at baseline will continue RT-PCR testing, as per schedule of assessments, until they become positive or reach the planned end of study. When RT-PCR positivity is confirmed, participant will self-isolate according to local requirements.
- (e) Participants who have been tested positive at the screening with a quick antigen test will be screen failed. In addition, any unscheduled test performed by the participant during the study will also be collected,
- (f) Serology COVID-19 (antibodies levels). In addition, any unscheduled test performed by the participant during the study will also be collected).

(g) Haematology, Biochemistry, Urine pregnancy test,	for details on the parameters evaluated. Pregnancy testing must be highly sensitive, at leas
before first administration.	-

- (i) Participants will receive their diary on D1 and keep it for the duration of the treatment to record data collected between D1 and D28. They will bring it back to the site on D28.
- (J) Additional follow-up remote or on-site unscheduled visits, may be required if deemed necessary by the investigator, notably in case of emerging or prolonged adverse events. During the unscheduled visit, the investigator will evaluate the WHO COVID-19 scale and the NEWS-2 scale, in addition to any assessments deemed necessary.

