4.1.2 Missing data

In general, an observed cases approach will be applied in case of missing data, i.e., only the observed subject data at a given timepoint will be used.

There will be one notable exception to this rule for the primary efficacy endpoint: if a subject discontinued the study without a confirmed negative test result on D28 (and on any day in between), then the missing data will be imputed using a multiple imputation (MI) method, under the assumption that the results are missing at random (MAR). Details on the MI method can be found in section 4.6.1. The MI method will only be used for the primary efficacy endpoint.

Missing/incomplete information related to AEs and concomitant medications will be handled as listed below, when applicable. Following these steps using temporary programming will ensure that missing date imputation uses the most conservative approach.

In case of a (partially) missing onset date, and the end date is determined to be after the first date of study drug administration, the onset date will be imputed as follows:

• Partially missing onset date:

Statistical Analysis Plan	Version 1.0		Page 11 of 25
Sponsor	MedinCell	Protocol No	mdc-TTG-CT-002

- If the day part is missing and month is equal to month of first study drug administration, then day will be set to day part of first study drug administration date.
- o If the day part is missing and month is not equal to month of first study drug administration, then day will be set to the first day of that month.
- o If both day and month part are missing, and year is not the same as the year of the first study drug administration, then day and month will be set to 1 January.
- o If both day and month part are missing, and year is the same as the year of the first study drug administration, then day and month part will be set to day and month of first study drug administration.
- Complete missing onset date:
 - o If the end date is on or after date of first study drug administration, then the onset date will be set to the date of first study drug administration.
 - o If the end date is prior to the date of first study drug administration, then the onset date does not need an imputation, and the event or medication is considered a pre-treatment AE or prior medication.

In case of a (partially) missing end date, the end date will be imputed as follows:

- In case end date is partially missing:

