4.6.2 Secondary endpoints

Statistical Analysis Plan	Version 1.0		Page 15 of 25
Sponsor	MedinCell	Protocol No	mdc-TTG-CT-002

The analysis of the secondary endpoints is purely explorative.

Results of RT-PCR tests and time to a positive test will be performed on the mFAS and PP population, while the analysis related to the occurrence of symptoms, (related) adverse events are performed on the FAS and PP population.

Treatment comparisons on proportions will be done using Cochran Mantel Haenszel chi-square test presenting odds-ratios, relative risk, and risk differences with 95% confidence intervals. Country will be used as a stratification factor. In case the study was only performed in one country, the Chi-squared/Fisher's exact test will be used.

Comparisons between treatment groups on time to events will be done by using a Cox proportional hazard model, under the assumption of proportional hazards. Time-to event curves will be created for visualization. Hazard ratios with 95% CI will be presented, together with the P-values. Censoring will be at study completion or at discontinuation date (including date of death, if occurring).

Treatment comparisons on mean score (WHO COVID-19 and NEWS-2) will be performed per time point by means of the t-test. If normality cannot be assumed based on visual inspection, a non-parametric alternative will be used.

Statistical Analysis Plan	Version 1.0		Page 16 of 25
Sponsor	MedinCell	Protocol No	mdc-TTG-CT-002

Treatment comparisons on durations will be examined by means of the non-parametric Wilcoxon-Rank-Sum test. If normality can be assumed based on visual inspection, a parametric alternative will be used.

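### Time to positive RT-PCR: on the supplied text, the censoring rule in SAP 4.6.2 counts a retained participant with no D28 PCR as event-free at D28 (minor, exploratory endpoint)

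*SAP*

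**What the plan says.** SAP 4.6.2 compares time-to-event endpoints with a Cox model and presents hazard ratios, confidence intervals, P-values and curves for visualization. It gives one censoring rule: "Censoring will be at study completion or at discontinuation date (including date of death, if occurring". Time to positive RT-PCR falls under it: "Results of RT-PCR tests and time to a positive test will be performed on the mFAS and PP population". The section also states that "The analysis of the secondary endpoints is purely explorative".

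On testing, footnote (d) to the protocol's Schedule of Assessments has "PCR test to be performed on D1, D4, D7, D10 and D28", and baseline-negative participants "continue RT-PCR testing, as per schedule of assessments, until they become positive or reach the planned end of study". The schedule shows no PCR at the D56 end-of-study visit. Unscheduled tests also count; the synopsis lists "RT-PCR tests on D4, D7, D10, and D28, and at any unscheduled visits". The D28 visit has a +2-day window and may be held remotely.

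On missing data, SAP 4.1.2 sets an observed-cases principle, under which "only the observed subject data at a given timepoint will be used", and confines imputation: "The MI method will only be used for the primary efficacy endpoint". SAP 3.3 and 3.4 admit a baseline-negative participant to the mFAS after one tablet and one post-randomisation efficacy assessment, so a missed D28 PCR does not exclude anyone. SAP section 4 refers to section 6.1 for derived data; that section is not in the supplied text.

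**The concern.** For a clinical event, follow-up to the end of the study does observe event status. For a PCR endpoint, status is known only when a test is done. Between D10 and D28 there is an 18-day gap with no scheduled test. Someone negative on D10 with no D28 PCR and no unscheduled test has unknown status over that gap, yet the written rule keeps that person in the D28 denominator and can never place the person in the numerator. That lowers the curve. If the two arms miss D28 at different rates, it also moves the hazard ratio.

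The rest of the supplied text does not settle the matter. The observed-cases principle argues against reading an unobserved D28 result as negative, but it sets no censoring date. Multiple imputation is reserved for the primary endpoint.

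At stake are the curve and hazard ratio of the first-listed secondary objective.

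**Working it through.** **The plan's own figure.** The documents give no event count or power for time to positive RT-PCR. The only related figure is the primary sample size, with 54% v 34%, two-sided 5% and 90% power. With A = [1.96·√(2·0.44·0.56) + 1.2816·√(0.54·0.46 + 0.34·0.66)]² = 5.09 and d = 0.20, the continuity-corrected n = A[1 + √(1 + 4d/A)]²/(4d²) = 137.2, so 138 per arm; 138/0.70 = 197.1, so 198. Both match the plan, and neither depends on this censoring rule.

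**Inputs.** From the documents: D28 positivity P28 of 54% (placebo) and 34% (ivermectin), and the visit days. Assumed, because the documents give no figures: the share s of cumulative hazard falling by D10 (80%, 50%, or 10/28 = 36%, a constant hazard); the share m missing the D28 PCR among those still in the study (5 or 10%); and, at first, no unscheduled tests. The +2-day window and remote option favour low m.

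**Written rule.** P10 = 1 − (1 − P28)^s, and the D28 curve reads P10 + (1 − m)(P28 − P10). Example, placebo, s = 0.5, m = 0.10: P10 = 1 − √0.46 = 0.3218; curve = 0.3218 + 0.9 × 0.2182 = 0.518.

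| D28 curve, written rule | s = 80% | 50% | 36% |
|---|---|---|---|
| Placebo, 5% missed (truth 54%) | 53.6 | 52.9 | 52.5 |
| Placebo, 10% missed | 53.2 | 51.8 | 51.0 |
| Ivermectin, 10% missed (truth 34%) | 33.4 | 32.5 | 32.0 |

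**Last-negative rule.** Let q = (P28 − P10)/(1 − P10), and let mi and mu be the missed shares among those infected after D10 and those still uninfected. The curve is 1 − (1 − P10)(1 − q′), with q′ = q(1 − mi)/[q(1 − mi) + (1 − q)(1 − mu)]. If mi = mu, then q′ = q and the curve returns 54% and 34%.

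**Hazard ratio under the written rule.** Expected counts in a Cox model (Efron ties, 140 per arm = 200 × 0.70, hazard to D10 split 4:3:3 over D4, D7 and D10):
- No true effect, equal 10% missed: 1.00.
- No true effect, 5% missed on placebo and 10% on ivermectin: 0.992 / 0.976 / 0.965. A simulation gave 0.994 / 0.975 / 0.964, with the nominal 5% test rejecting 4.9 / 5.2 / 5.4%.
- Planned effect, true HR = ln 0.66/ln 0.46 = 0.535, equal 10% missed: 0.536 / 0.538 / 0.541.

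**Where last-negative censoring is not better.**
- *Skipping related to infection (placebo, s = 0.5).* Infected miss 10%, uninfected 30%: written 51.8, last-negative 57.9, so the written rule is closer. Infected miss 30%, uninfected 10%: 47.5 and 50.5, so last-negative is closer and both read low. With mi = 10%, the placebo break-even is mu = 20 / 22 / 24%.
- *Unscheduled positives with equal skipping.* Let a share u of infected D28-missers have an unscheduled positive by D28. The written rule reads P10 + (1 − m + mu)(P28 − P10), where mu here is m × u. Under last-negative, events are e = q(1 − m + m·u) and the risk set is e + (1 − q)(1 − m). Placebo, s = 0.5, m = 0.10, u = 0.5: written 0.3218 + 0.95 × 0.2182 = 52.9%. For last-negative, e = 0.3057, risk set = 0.9161, ratio = 0.3337, curve = 1 − 0.6782 × 0.6663 = 54.8%. At u = 0.7 the pair is 53.4 and 55.1. The written rule becomes closer once u exceeds 0.52 / 0.58 / 0.60 (placebo) or 0.50 / 0.53 / 0.54 (ivermectin).

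**The case against.** The strongest objection is that this depends on text that was not supplied. Time to positive RT-PCR is a derived variable, so its dates would be expected in section 6.1, and 4.6.2 itself looks incomplete around page breaks. This stands: the point is conditional on 6.1, and a reader should not infer that the plan lacks a PCR-specific rule.

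Second, little follows from it. The endpoint is exploratory, and the curve shifts by 0.4 to 3.0 points on placebo under the assumed rates. A reader might infer a material bias in the treatment effect. With 10% v 30% missed and no true effect, the hazard ratio would be 0.97 / 0.90 / 0.86 (0.86 at constant hazard). But no passage supports such an imbalance. The 30% in the sample-size text covers dropout or participants not evaluable for the primary analysis, and those who discontinue are already censored when they leave.

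Third, a reader might infer that last-negative censoring is simply correct. It is not. An infected D28-misser with an unscheduled positive stays in as an event, while one without a positive is removed, which pushes the curve up even with equal skipping. This stands and must be stated with the fix.

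Fourth, the fix is partial: participants negative at D28 are still followed to D56 with no scheduled PCR. This also stands.

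**Conclusion.** The point holds on the supplied text, as a minor matter with a cheap improvement; confidence is low to medium because section 6.1 is unseen. The written rule keeps retained participants with no D28 PCR in the D28 risk set as event-free. Under 5 to 10% missed and no unscheduled tests, the placebo curve reads about 51.0 to 53.6% instead of 54%. The hazard ratio barely moves with equal missingness and is about 0.965 to 0.993 under the null with 5% v 10% missed. Missed-test rates, infection timing and the share with unscheduled positives are all assumptions.

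When infected and uninfected participants skip D28 equally within an arm, the written rule reads low and the last-negative rule reads at or above the truth, so the two together bracket it. That bracket is not guaranteed otherwise: if infected participants skip more often, both can read low. The documents do not support any inference that the primary analysis or the sample size is affected.

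**What to change.** First check section 6.1. If it already gives a PCR-specific censoring date, nothing more is needed. If not, add to SAP 4.6.2, for time to positive RT-PCR only: participants with no positive RT-PCR and no RT-PCR at the D28 visit are censored on the date of their last negative RT-PCR, scheduled or unscheduled. Participants with a negative D28-visit PCR and all clinical-event endpoints keep the current rule, and unscheduled positives up to study completion remain events. Always report the current rule alongside as a sensitivity analysis.

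The limit to participants with no D28-visit PCR matters because of the +2-day window. If everyone were censored on the actual date of the last negative test, the few tested last would form the whole risk set. With an assumed 80/10/10% tested on D28/D29/D30, the placebo curve would be 1 − (1 − P10)(1 − 0.8q)(1 − 0.5q)(1 − q) = 62 / 71 / 75% instead of 54%.

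State the downsides in the SAP. The rule assumes that missed tests are unrelated to infection within arm, in line with the missing-at-random assumption of the primary imputation. It is not closer to the truth if uninfected participants skip D28 about twice as often as infected ones. Even with equal skipping, the same is true if more than about 50 to 60% of infected D28-missers have an unscheduled positive. It does nothing about the absence of scheduled PCR between D28 and D56.

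The cost is one SAP sentence, a short caveat, minor programming and one extra output, with no new data. It should be settled by SAP amendment before database lock and unblinding.

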	If the close contact wishes to participate in the study, they should ask the primary contact if they agree to give their informed consent by signing the form attached to the leaflet, through which primary cases agree that information related to their positive testing will be collected as evidence. Then, the contact case should get in touch with the study site and arrange for an appointment for the screening visit (within 5 days after the contact with the index case). At that appointment the contact will be screened, and they will provide the study staff with the index case's signed consent form and positive PCR test result. In addition, informed consent from the close contact must be obtained. If all eligibility criteria are met, the participant (close contact) will be randomised and a loading treatment dose will be administered. Participants will be assigned in a 1:1 ratio to receive oral daily treatment with either ivermectin or placebo. The study requires two visits to the study centre, on Day 1 and Day 28, the first and last days of treatment. In addition, there will be at least 3 remote visits that can be conducted by telephone. The treatment period lasts for 28 days in total, followed by a 28-day follow-up period, and there is a 2-day window period for visits. Therefore, total study duration for each participant is up to 58 days.			
Study Population:	Healthy volunteers between 18 and 65 years old, self-isolating after being in close contact with an individual who has had a documented exposure to COVID-19 within a maximum of 5 days prior to Screening.			

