Inclusion Criteria:	 Individuals who meet all of the following criteria are eligible to participate in the study: Age between 18 and 65 years, inclusive. Body weight >45 kg. Body Mass Index >18.5. Close contact with a person who has a PCR-confirmed SARS-CoV-2 infection within 5 days before screening. Only one member in the same household will be enrolled. Participants must be able to give informed consent and comply with the study's scheduled events/visits and study assessments. SARS-CoV-2 positive index case must be able to give consent to enable collection of the documented positive PCR test. Female participants of childbearing potential must use a highly effective method of contraception for the duration of the trial. Their male partners should also use a contraception method (i.e condom) unless vasectomized. (Refer to section 4.5 Contraception Requirements). Male participants must use a contraception method (i.e condom) for the duration of the trial, unless vasectomized. Their female partners, if they are of childbearing potential, must use a highly effective method of contraception. (Refer to section 4.5 Contraception Requirements). 			

Exclusion Criteria:	Individuals who meet any of the following criteria are not eligible to			
	participate in the study:			
	1. Pregnant or breast-feeding.			
	2. Participants who have been administered COVID-19 vaccine			
	prior to the inclusion or have a planned vaccination during			
	the duration of the study.			
	3. A positive COVID-19 result (PCR or antigen test) within 8 days of screening.			
	4. Presence of typical COVID-19 symptoms (fever >38°C,			
	SpO2 below 93%, dyspnoea, difficulty breathing, chills,			
	repeated shaking with chills, ageusia, anosmia, cough,			
	myalgia, headache) in the past 48 hours prior to screening.			
	5. Presence of a known uncontrolled/unstable clinically			
	significant medical condition, considered by the investigator			
	as incompatible with study participation.			
	6. Known history of HIV, HBV and/or HCV.7. Hypersensitivity to any component of ivermectin.			
	J1 J J 1			
	8. Participants who have been administered ivermectin within 30 days prior to screening.			
	9. Participation in another interventional trial within the last 30			
	days or 5 half-lives of the IMP of the other trial, whichever			
	comes first.			
	10. Having undergone extensive bowel resection which may			
	alter ivermectin absorption.			
	11. Participants with gastrointestinal erosions and ulcers (e.g.			

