4 STATISTICAL ANALYSES

All statistical analyses will be performed using the SAS® software (Version 9.4 or later, SAS institute, North Carolina, USA).

All descriptive statistics will be given by treatment group. For baseline and basic variables, they will also be given for the entire analysis set. Screening failure data will not be analysed.

If not stated otherwise the following standard types of descriptive analyses will be presented:

- Descriptive statistics for continuous data

Statistical Analysis Plan	Version 1.0		Page 10 of 25
Sponsor	MedinCell	Protocol No	mdc-TTG-CT-002

N, mean, SD, min, lower quartile, median, upper quartile, and max will be presented. These descriptive statistics will be determined for measured values and optionally for differences to baseline.

Descriptive statistics for categorical data

Absolute frequencies and percentages will be presented. Percentage bases (denominators) will be identified in the table title or footnote (i.e. all subjects at risk, all cases). For changes from baseline, shift tables may be generated.

Inferential statistics

Unless otherwise stated, all statistical tests will be performed two-sided and at a type I error probability of α =0.05.

Unless otherwise stated, all confidence intervals (CIs) will be derived two-sided and at a confidence probability of $1-\alpha=0.95$.

Listings

All recorded data will be listed by subject sorted by treatment group. Identification variables are centre number, participant number and treatment.

Derived data will be stored in special analysis data sets and will be calculated as outlined in section 6.1.

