4.1 Conventions

4.1.1 Baseline definition

Results obtained on D1 (Screening/Randomization) of the study are considered as baseline results. In case of more than one result the closest to start of treatment will be used.

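### The SAP compares unadjusted WHO COVID-19 and NEWS-2 means, while the protocol's endpoint is change from baseline; adjusting for D1 score and country would align the two at almost no cost

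*SAP*

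**What the plan says.** The protocol synopsis lists "Change from baseline in the WHO-COVID 19 and NEWS-2 scores" among the secondary endpoints. Its evaluation criteria schedule "WHO COVID-19 and News 2 scales scoring on D1, D10, and D28, and at any unscheduled visits", and Table 1 shows the same three planned visits. A D1 score is therefore planned for every participant.

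SAP 4.6.2 gives the inferential analysis: "Treatment comparisons on mean score (WHO COVID-19 and NEWS-2) will be performed per time point by means of the t-test". A non-parametric test takes over if a visual check does not support normality. Neither sentence names a change score, a D1 covariate or a country term. In the same section, comparisons of proportions are stratified by country, and SAP 1.3 makes country the randomisation stratum.

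Baseline does appear elsewhere. SAP 4.1.1 fixes it: "Results obtained on D1 (Screening/Randomization) of the study are considered as baseline results". SAP 4 lets change be described: "These descriptive statistics will be determined for measured values and optionally for differences to baseline". SAP 4.6.2 also sets the standing of these analyses: "The analysis of the secondary endpoints is purely explorative".

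**The concern.** The protocol names one quantity and the SAP's test is written for another. The report would show a p-value for mean scores beside an endpoint defined as a change, with nothing to say how they relate. SAP section 5 states that the methods were checked for consistency with the protocol, so the difference should be removed or explained.

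The second stake is precision. If the D1 score predicts later scores, leaving it out wastes information that is already collected. D1 scores are not guaranteed to be constant:

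- Exclusion criterion 4 looks back only 48 hours and partly works by thresholds (fever above 38°C, SpO2 below 93%), so lesser abnormalities can enter.
- A negative baseline RT-PCR is required for the mFAS (SAP 3.4) but not for the FAS (SAP 3.3).
- SAP 4.6.2 places symptom analyses on the FAS and PP set. It does not name the two scales in that sentence, but they are the natural measure for the symptom objective.

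**Working it through.** **1. The plan's own figure.** The documents give no sample size, SD or correlation for the scores. The only planning figure is for the primary endpoint: 54% against 34%, two-sided 5%, 90% power.

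- Uncorrected: n′ = [1.960·√(2·0.44·0.56) + 1.282·√(0.54·0.46 + 0.34·0.66)]² / 0.20² ≈ 127.4, rounded up to 128.
- Continuity-corrected: n = (n′/4)·[1 + √(1 + 4/(n′·0.20))]² ≈ 137.2, rounded up to 138.
- Allowing for 30% not evaluable: 138/0.7 = 197.1, rounded up to 198.

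The stated 138 and 198 per arm reproduce. This point does not touch them; 138 per arm is used below only as an illustrative size.

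**2. Is the expected difference altered?** Let Y be the follow-up score and B the D1 score. The between-arm difference in mean change is the difference in mean Y minus the difference in mean B. Randomisation makes the second term zero on average, so raw and change comparisons target the same mean difference.

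**3. Precision.** Let ρ be the correlation of D1 with follow-up and k = SD(D1)/SD(follow-up). Variances relative to the raw t-test are:

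- ANCOVA: 1 − ρ².
- Change-score t-test: 1 + k² − 2ρk, which is below 1 only if ρ > k/2.

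For power, set the effect so that the raw t-test has 80% with 138 per arm: δ = (1.960 + 0.842)·√(2/138) = 0.337 SD. With relative variance v, power is Φ(2.802/√v − 1.960). All values of ρ and k are assumptions. Cells show v, with power in brackets.

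| ρ | ANCOVA | Change, k = 0.25 | Change, k = 0.5 | Change, k = 1 |
|---|---|---|---|---|
| 0 | 1.00 (80.0%) | 1.06 (77.6%) | 1.25 (70.7%) | 2.00 (50.8%) |
| 0.1 | 0.99 (80.4%) | 1.01 (79.5%) | 1.15 (74.3%) | 1.80 (55.1%) |
| 0.3 | 0.91 (83.6%) | 0.91 (83.5%) | 0.95 (82.0%) | 1.40 (65.8%) |
| 0.5 | 0.75 (89.9%) | 0.81 (87.5%) | 0.75 (89.9%) | 1.00 (80.0%) |

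**4. A setting closer to this population.** A simulation (138 per arm, 2,000 replicates) gave a share of participants a D1 score of 1 and the rest 0. Infection was 54% against 34%. Infected participants scored 1, 2 or 3 at follow-up with probabilities 0.5, 0.4 and 0.1, and uninfected participants scored 0. A non-zero D1 score added 0, 0.5 or 1 to the follow-up score. All score values are assumed.

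- The mean difference was about −0.32 for raw, change and ANCOVA alike.
- With 5–10% non-zero at D1, ANCOVA/raw variance was 0.90 to 1.00, and change/raw variance was 0.90 to 1.09.
- With nobody non-zero at D1, all three coincided.

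**5. Why ANCOVA serves the protocol endpoint.** Subtract B from both sides of Y = a + τ·treatment + β·B + γ·country. This gives Y − B = a + τ·treatment + (β − 1)·B + γ·country. The estimate of τ and its standard error are identical. The identity does not carry over to ranks, because ranks of follow-up scores are not ranks of changes.

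**6. Country.** The documents give nothing from which to size its effect on the scores.

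**The case against.** The strongest reply is that the SAP's test is valid and that ANCOVA is a preference. Much of this stands. A t-test on randomised arms is unbiased for the difference in mean change, and its standard error already covers chance imbalance at D1. A reader might infer that the SAP estimates a different treatment effect; step 2 shows that it does not.

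A reader might also infer a material loss of power. The documents do not support that. Participants are "Healthy volunteers between 18 and 65 years old, self-isolating after being in close contact", exclusion criterion 4 begins "Presence of typical COVID-19 symptoms (fever >38°C" and goes on to cough, dyspnoea and others, and contacts who are antigen-positive at screening are screen failures. Baseline PCR-positive members of the FAS must pass the same filters. Little spread at D1 is likely, and showing that D1 can vary does not show a useful correlation. Following the protocol's wording literally, with a plain change score, could even lose precision.

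Third, it would be too strong to say that the SAP ignores D1 throughout. It defines baseline and permits descriptive change, and SAP 4 refers derived data to a section 6.1 that is not in the public text and may derive change. That absence is no fault of the plan. What survives is narrower: even if 6.1 derives a change score, the test stated in 4.6.2 is on the mean score, without D1 or country.

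The country point is also modest. The SAP foresees a single-country trial, in which case it falls away.

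**Conclusion.** The point holds as a minor misalignment with a possible small loss of precision. The stated comparison does not match the named endpoint and leaves out both the D1 score and the randomisation stratum. It is not a bias. That conclusion rests on randomisation, and on missing follow-up not selecting differently on D1 score in the two arms.

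The variance saved by D1 adjustment is ρ²: 1%, 9% or 25% at assumed ρ of 0.1, 0.3 or 0.5. Given the entry criteria, the lower part of that range is more plausible, and the simulated settings with 5–10% non-zero D1 scores gave about 0–10%. The endpoint is exploratory, so sample size, type I error and the primary conclusion are unaffected.

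**What to change.** Replace the score sentence in SAP 4.6.2 with wording to this effect: at D10 and D28, each score is analysed by ANCOVA with treatment, D1 score and, if more than one country enrols, country; the adjusted treatment difference is reported with its 95% CI. Note that the linear model gives the same treatment estimate for the score and for its change from D1, so it addresses the protocol endpoint.

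Do not substitute a plain change-score t-test, which is less precise than the raw test when ρ < k/2. If normality fails, use a rank-based analysis adjusted for D1 score and stratified by country, without claiming that it equals an analysis of change. If the sponsor prefers to keep raw means, the minimum is one sentence saying why they stand in for the protocol's change from baseline.

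The cost is a short text change. The D1 scores and country are already collected, and SAP section 2.1 provides for amendment before database lock and unblinding. If D1 scores prove constant, the D1 term drops out and nothing is lost.
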